Grant Number: UH3DA047793

Title: tDCS to Decrease Opioid Relapse

MPIs: [name] and [name]

Medical Monitor: [name]

2. Summary of the Protocol:

2.a, 2.b Brief Description of the Protocol, Primary and Secondary Outcome Measures

This study has two phases. In phase one (UG3), we propose to use functional magnetic resonance imaging (fMRI) and electroencephalographic (EEG) to quantify changes in brain function and reported craving before and after administration of five sessions of transcranial direct current stimulation (tDCS) targeting the right dorsolateral prefrontal cortex (DLPFC). Opioid dependent participants (n=60) who recently initiated buprenorphine or methadone will be randomized to tDCS+Cognitive Control Network (CCN) priming stimulation vs. sham tDCS+CCN priming. Participants in their first month of prescribed buprenorphine or methadone will be assessed using fMRI and EEG, once prior to tDCS and again one week later after completion of 5 sessions of tDCS+CCN priming. With a focus on the craving outcome, we will use two task-based fMRI paradigms that challenge networks associated with craving (CR) and cognitive control (CCN), and will examine these and the salience network using resting state functional connectivity. We examine an additional validation measure of the effect of tDCS on the DLPFC – an oscillatory target -- EEG frontal theta power during working memory(WM). In this UG3 phase, fMRI and EEG will be expected to provide 1) validation of expected network and oscillatory changes from tDCS-targeting and 2) an effect size for DLPFC vs sham stimulation. Go/no go criteria for the UG3 phase will be demonstration of greater fMRI change in any node of the CR or CCN networks or enhanced frontal theta power during a WM task AND greater change (at least 10% difference between conditions, controlling for baseline craving) in subjective craving measured during a cue reactivity task or outside the fMRI following the tDCS+CCN priming intervention compared to sham tDCS+CCN priming.

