The optimal frequency, duration and number of tDCS sessions to maximize effects on craving, or any other construct in this young field, remain obscure. We chose to deliver 5 sessions of tDCS because this number has been used in prior successful tDCS craving interventions and must be balanced against adherence concerns. While we are hopeful that participants will complete 5 consecutive days of tDCS, the interruption of weekends and the transition from the ADP setting (where the tDCS protocol will start) where days are structured, to the community setting, raises the possibility of missed tDCS sessions and therefore we will allow these 5 sessions to occur over 10 days if necessary, as has been described in prior studies, tracking both average number of sessions received and period of treatment for analyses. The sham tDCS condition is included in our design to separate the effects of ongoing opioid treatment from the effect of active tDCS on craving. We decided not to include a third no-tDCS arm, as this would omit any nonspecific treatment effects (match for attention, expectation) of entering a neurostimulation treatment protocol. This protocol will provide a basis for future studies of tDCS stimulation parameters (frequency, duration, number) that could optimize adherence and treatment effects of drug use outcomes.

In phase two (UH3), we will perform a larger RCT using the same treatment protocol in 100 opioid dependent participants who recently initiated buprenorphine or methadone. Participants will be randomized to receive five sessions of tDCS+CCN priming stimulation vs. sham tDCS+CCN priming. Phase two will address long-term (3-month) neurobehavioral outcomes, including opioid relapse, craving, and sustained fMRI changes during a paradigm that challenges networks associated with craving (CR) and cognitive control (CCN). During the 12 weeks of opioid maintenance treatment, we will examine our primary clinical outcome, relapse (opioid use on >4 days per month and having an opioid positive urine screen), as well as days of opioid use.

2.c Inclusion/Exclusion Criteria:

UG3/UH3 Inclusion Criteria: (a) current opioid dependence, (b) between 21-50 years of age, (c) recent initiation of buprenorphine or methadone (<30 days)

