Exclusion Criteria: (a) diagnosis of organic brain disorder, bipolar disorder, schizophrenia, schizo-affective, schizophreniform, or paranoid disorder, (b) current suicidality, (c) evidence of neurocognitive dysfunction, (d) contraindications for tDCS (e.g seizure disorder), (e) probation/parole requirements or an upcoming move that might interfere with protocol participation, (f) planning to terminate buprenorphine or methadone in less than 3 months, and (g) scalp lesions near the tDCS electrode sites.

Exclusion Criteria related to FMRI scanning are: (a) history of neurological disorder (e.g., epilepsy, stroke, brain injury with loss of consciousness>10 min), (b) impaired uncorrected vision, and (c) MRI contraindications (e.g., claustrophobia, specific metallic implants and injuries, and pregnancy).

tDCS-related considerations: Careful consideration will be given when determining whether tDCS is safe for potential participants. Additional exclusion criteria related to tDCS include: metal implanted in the cranial cavity, pacemaker, poor cognitive functioning (i.e., Alzheimer's disease or dementia), history of neurological disorder (e.g., epilepsy or other seizure disorder), or other significant or chronic medical conditions that affect the brain (e.g., Parkinson's disease, Huntington's disease, multiple sclerosis, traumatic brain injury). [name] will have the final decision regarding whether a participant is medically stable enough to engage in this trial.

2.d Power Calculation and Sample Size:

In the UG3 phase of this project, we plan to enroll 60 participants. With an expected attrition rate of 20% (data loss over two sessions due to poor performance or movement artifact—a conservative estimate that is a larger loss than in our ongoing FIRST study), our final sample size will be 48, or 24 per group. This number provides 82% power for the expected effect size of .75, chosen based on prior tDCS studies and our belief that a large effect size should be required to continue to the UH3. In the UH3 phase, we again anticipate a 20% attrition rate over the 5 tDCS sessions and initial two fMRI scans. If the third scan (at 4 weeks) is missed, we expect this will be due to treatment drop-out or relapse. With 100 participants enrolled, we will have a final sample of 80 patients which provides a power of .8 to detect a group difference in relapse between relapse and sham of 15% vs 39% at 3 months follow-up.

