1) CR: Two 2x2 mixed ANOVAs will be used to determine whether mean response to cues during CR decline across nodes of the craving network (VS, amygdala, VMPFC), including salience network (AI, ACC) and increases in the CCN (MFG, IPL). Significant pre-post main effects and group x treatment interactions are predicted in each. Those who received tDCS+CCN priming are expected to exhibit greater change. Follow up analyses of individual nodes within each network and whole-brain voxel-wise contrasts will be conducted to inform phase 2 analyses.

2) n-Back: Two 2x2 mixed ANOVAs will be used to determine whether mean response to the n-Back challenge increases across nodes of the CCN (MFG, IPL) and the salience network (ACC and AI). Significant pre-post main effects and group x treatment interactions are predicted in each. Those who received tDCS are expected to exhibit greater change. Follow up analyses of individual nodes within each network and whole-brain voxel-wise contrasts will be conducted to inform phase 2 analyses.

3) Resting state: Two 2x2 mixed ANOVAs will be used to determine whether mean network coherence (functional connectivity) decreases across nodes of the craving network (VS, amygdala, VMPFC), including the salience network (AI, ACC) and increases in the CCN (MFG, IPL). Significant pre-post main effects and group x treatment interactions are predicted

in each. Those who received tDCS are expected to exhibit greater change. Parallel exploratory analyses will be conducted to examine resting state functional connectivity of the salience network and DMN.

In the UH3, neuroimaging analyses will generally parallel those described for UG3. We will use a 2x3 ANOVA (three time points) to test the hypothesis that tDCS+CCN priming will be superior to sham tDCS+CCN priming on both subjective and fMRI measures of craving and cognitive control at the end of 5 sessions and at 3-months post tDCS. This same analytical method will be used to test the effect of intervention on days of drug use at the end of 5 sessions and at 3-months. We will use the Pearson χ^2 -test of independence to compare tDCS+CCN priming to sham tDCS+CCN priming on relapse at 3-months.

FMRI data analyses

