A priori task-based FMRI ROI analyses will be our primary method for quantifying changes in the craving, salience and cognitive control networks and subsequent hypothesis testing, while analyses involving the functionally defined ROIs will serve to validate our a priori findings. Mean task-related effect will be determined for each ROI of each individual for each condition of each task by averaging all voxels of each ROI. Results of these quantifications will be used as dependent measures in hypothesis testing. In primary analyses, mean effects will be examined across all nodes of each network, followed by analyses of each network node. Functional connectivity analyses will be performed on all networks during crosshair fixation (resting). We will use the seed region method. Briefly, BOLD signal will be averaged from four 3mm³ seed voxels at the center of mass of each ROI of each network (see Table 1) and extracted for each of the time points acquired. These reference series files will be used as predictors in one voxel-wise GLM analyses per ROI to identify the strength of the relationship between each brain voxel and the average of the seed region over time. Each a priori region will serve as a seed region once for its particular network. After Fischer's transformation from r-values to z-values, the resulting mean voxel-wise values will be averaged in each target node (i.e., ROI not serving as the seed) following each GLM. For CR, these target ROI averages will then be averaged across two seed region iterations (i.e., excluding the seed region; this step is not needed for the 2 ROI salience networks). The resulting means for the nodes of each network will be averaged across ROIs (3 for craving, 2 for salience, 3 for CCN) to derive a network coherence metric. Substance use type (heroin, prescription pills) will be included as a covariate in statistical models.

EEG analyses.

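### The primary UH3 relapse test is an unadjusted chi-square although plausibly prognostic baseline variables are collected: prespecified adjustment is a cheap gain of uncertain size

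*Combined protocol and SAP*

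**What the plan says.** Section 2 (brief description of the UH3 phase) names the endpoint: "we will examine our primary clinical outcome, relapse (opioid use on >4 days per month and having an opioid positive urine screen"). The only test given for it, in section 4.c, is a Pearson chi-square "test of independence to compare tDCS+CCN priming to sham tDCS+CCN priming on relapse at 3-months". No covariate or stratification factor is attached to it.

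Section 2.d sets the size of the trial: "With 100 participants enrolled, we will have a final sample of 80 patients". The power claimed for that number is 0.80, with assumed rates given as "a group difference in relapse between relapse and sham of 15% vs 39% at 3 months follow-up". It states neither alpha nor sidedness.

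Baseline information is used in three other places:
- Section 2.a/2.b: the UG3 go/no-go craving criterion is assessed "controlling for baseline craving".
- Section 4.c, under FMRI data analyses: "Substance use type (heroin, prescription pills) will be included as a covariate in statistical models".
- Section 4.c, under EEG outcome measures: the models include the baseline value of the outcome, plus variables that differ by arm or predict attrition.

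**The concern.** The most important comparison in UH3 is the one for which the plan names no baseline information. Several candidate covariates exist. Subjective craving is analysed at three time points in UH3, so a baseline value is taken. Substance type is recorded. Buprenorphine or methadone is known from eligibility. A baseline value for days of opioid use is only implied, because that outcome is to go through the same three-time-point ANOVA.

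In a randomised comparison, adjusting for a variable that predicts relapse sharpens the treatment contrast and guards against chance imbalance, which can be material at 40 per arm. The cost of leaving it out is power, in a trial that has none to spare under a two-sided test.

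**Working it through.** **Inputs.** From section 2.d: 100 enrolled, 20% attrition, 80 analysed, relapse 15% and 39%, stated power 0.80. Assumed because not stated: 1:1 allocation (40 per arm, as in the equal UG3 split), alpha 0.05, and 15% as the active arm.

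**Step 1: the plan's own figure.** With mean rate 0.27 and difference 0.24:
- Null SE = √(2 × 0.27 × 0.73 / 40) = 0.0993
- Alternative SE = √((0.15 × 0.85 + 0.39 × 0.61) / 40) = 0.0956
- Power = Φ((0.24 − z × 0.0993) / 0.0956)
- One-sided 5% (z = 1.645): Φ(0.80) = 0.789. Arcsine gives 0.797 and unpooled 0.807. The stated 0.80 reproduces.
- Two-sided 5% (z = 1.960): Φ(0.475) = 0.683. Arcsine gives 0.697, unpooled 0.709 and exact Pearson 0.692. The stated 0.80 does not reproduce.

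The UG3 figure follows the same pattern: d = 0.75 with 24 per group gives 82.0% one-sided and 72.0% two-sided, against 82% stated. A Pearson chi-square at the 5% level is two-sided in effect, so the planned relapse test has about 68–69% power. Reaching 80% two-sided would take 53 per arm, that is 106 analysed and 106 / 0.8 = 132.5, rounded up to 133 enrolled.

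**Step 2: how many covariates the data can carry.** Expected relapses = 40 × 0.15 + 40 × 0.39 = 21.6. That supports one or two covariates, not more.

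**Step 3: the gain, by approximation.** If a covariate explains a share R² of outcome variance, the effective size is about 40 / (1 − R²) per arm. Two-sided power is then:

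| R² | Power |
|---|---|
| 0 | 68.3% |
| 0.05 | 70.6% |
| 0.10 | 72.9% |
| 0.15 | 75.4% |
| 0.20 | 78.0% |
| 0.25 | 80.6% |

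R² of about 0.24 is needed for 80%.

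**Step 4: the gain, by simulation.** One normal baseline covariate, 40 per arm, marginal rates 15% and 39%, logistic likelihood-ratio test. The unadjusted chi-square is at about 69% throughout. The nominal column is from 20,000 trials per cell. The last column sets the adjusted test to the same type I error as the chi-square, so that a slightly liberal test is not counted as a gain; its entries are good to about one point.

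| Odds ratio per SD (assumed) | Nominal adjusted power | At matched size |
|---|---|---|
| 1 | 70.4% | 69% |
| 1.5 | 71.2% | 70% |
| 2 | 73.4% | 73% |
| 2.5 | 75.6% | 75% |
| 3 | 77.9% | 76% |
| 4 | 80.5% | 80% |

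An odds ratio of 4 per SD corresponds to an AUC of about 0.80 within the sham arm.

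**Step 5: size of the adjusted test.** Under no treatment effect, the one-covariate likelihood-ratio test rejected in 5.3–5.5% of trials, against 4.6–4.9% for the chi-square. With two covariates it rejected in about 5.4–6.3%. A second covariate that predicts nothing also takes back part of the gain: at an odds ratio of 2 for the first, matched-size power was 70.4% against 69.2% for the chi-square.

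**The case against.** The strongest defence is that an unadjusted chi-square in a randomised trial is valid, simple, and suited to about 22 events. That stands: nothing here makes the planned inference wrong.

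Second, the benefit rests on prognostic strength that no document supplies. A reader might infer that strong predictors are being ignored. The documents do not support that. Section 2.d says effect sizes for baseline fMRI by later lapse are unavailable, and offers only that the constructs assessed are related to relapse in behavioural studies. With a weak predictor the gain is about one point.

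Third, a reader might infer that leaving out covariates is why the trial falls short of 0.80, or that adding them restores it. Neither follows. The shortfall arises because the power figure fits a one-sided test while the planned test is two-sided in effect. Only a very strong covariate would close the gap.

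Fourth, a reader might assume that adjustment has no effect on type I error. Step 5 shows a small inflation for the plain likelihood-ratio test, so the method for the p-value needs care.

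Finally, the substance-type sentence might be read as covering every model in the plan. It sits under FMRI data analyses, and a chi-square could not carry the covariate in any case.

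**Conclusion.** The point holds as a cheap improvement, not as an error. The primary relapse test uses no baseline information although usable variables exist. At matched type I error, one prespecified covariate loses essentially nothing if it proves useless. It adds about 1 to 4 points at odds ratios of 1.5 to 2 per SD, 6 to 7 points at 2.5 to 3, and about 11 points at 4, from a base of about 69%. The odds ratios are assumptions, as are 1:1 allocation, a two-sided 5% level and a normally distributed covariate. The mismatch between the stated 0.80 and the two-sided power must be corrected separately, by stating alpha and sidedness and revisiting the sample size.

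**What to change.** In section 4.c, prespecify as the primary relapse analysis a logistic regression on arm with baseline craving as covariate, or baseline days of opioid use if the sponsor confirms that it is collected. Allow at most one further named covariate, for example substance type or buprenorphine versus methadone, and fix the choice before unblinding; do not select by baseline significance tests as in the EEG plan.

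Report the standardised (marginal) risk difference with 95% CI, which stays on the scale of the 15% and 39% in section 2.d. Take the p-value from a re-randomisation test that mirrors the actual allocation scheme, or from another test whose size has been checked at 40 per arm. Keep the Pearson chi-square as a supporting analysis.

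The cost is a paragraph in the plan, slightly more analysis work and a strict cap on covariates. No extra patients or assessments are needed if the covariate chosen is already collected.

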EEG Data Processing. Semi-automatic preprocessing for artifact detection will be performed using the FASTER algorithm (Nolan, Whelan, & Reilly, 2010). This EEGLAB toolbox uses Welch methods and removes muscle, heart, motion, ocular artifacts, and other noise using a multiple step procedure consisting of a) bandpass and notch filtering, b) Independent Component Analysis (ICA), c) rejection and/or interpolation of bad channels/epochs. The final step of preprocessing includes visual inspection of the data rejecting any remaining artifactual epochs. Windows of 1400 ms (1100 -2500 ms after stimulus onset) will be included in analysis. Theta band (4 -8 Hz) power in frontal (Afz, Fz) electrodes will be averaged across both n-back levels.

Working Memory and EEG Summary Indices. Working memory performance at each assessment will be represented by d' to capture executive skills without influence by demographic variables, psychiatric status, or intelligence quotient (Haatveit et al., 2010). For each participant, and within each n- condition, values for d' will thus be calculated by dividing the difference of Z (false alarms) and Z ("hits") by the root mean square of 2; d' captures the participant's ability to discriminate between the two stimulus types (i.e., the 2-back target letters and the non-target letters). Difference in theta power between 0-back and 2-back conditions (Δtheta) will also be calculated at EEG/n-back assessment. Comparison of pre- versus post-treatment Δtheta will test the primary hypothesis that opioid dependent participants who received the active tDCS intervention will show greater increases in theta power after 5 intervention sessions than sham tDCS recipients. Estimation of power spectrum density (PSD) values in the beta band (13-30 Hz) will be computed and averaged from channels in four regions (frontal, central, temporal, and occipital-parietal) for analysis in relation to craving scores.

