EEG outcome measures analyses. We will conduct a repeated-measures ANCOVA with a within-subject factor of time (baseline and end-of-stimulation (EOS)), between-subject factor of intervention condition (active tDCS and sham) and covariates to test if there is a statistically significant difference in in the EEG outcome (Δtheta) across treatment groups. Pearson correlations will be used to examine beta PSD values in relation to craving scores. A separate ANCOVA with the same factors will be used to explore treatment group differences in resting state EEG beta PSD values. Covariates for both analyses will include the baseline measure of the evaluated outcome, as well as baseline variables found to vary significantly ($p < 0.05$) by intervention arm, or which significantly ($p < 0.05$) predict attrition at EOS. Post-hoc t-tests will be used to probe anticipated significant interactions.

5. Quality Assurance

All research personnel, will have formal training in research with human subjects (e.g., CITI training, NIH Human Subjects training). Drs. [name], [name], and [name] will provide training to and supervise research assistants. Research assistants will also have training in Good Clinical Practice.

Drs. [name] and [name] will be responsible for quality control of this study. They will review recruitment and retention reports, and AE reports on a weekly basis. The MPIs (or their designee) will inspect BL documents (consent forms, release of information) for completeness within a week after they are signed. The MPIs (or their designee) will also conduct protocol and data quality monitoring twice a year using a checklist. This monitoring will include reviewing other study records to ensure completeness.

6. Regulatory Issues

6.a, 6.c Reporting of SAEs, Non-Medication Trials

Drs. [name] and [name] will be responsible for overseeing the daily safety of all participants. There are several ways in which they will become aware of adverse events. First, research staff will ask participants about serious adverse events (as defined by Office of Human Research Protections (OHRP); e.g., inpatient hospitalization) at each research contact point (UG3: baseline, week 2 assessment, 5 tDCS appointments, 2 fMRI; UH3: baseline,

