Minimization. To minimize the risk of distress arising from the assessment procedure, only study staff that has been adequately trained in the assessment battery will complete all assessments, and senior study staff will supervise all assessment procedures. Individuals will also be advised that they may choose not to answer any question which they find upsetting. Further, during EEG and tDCS+CCN sessions, participants will be reminded they can stop the procedure at any time, if they get tired. All study procedures will be explained to the participants with an emphasis on the voluntary nature of the study. Furthermore, staff members will be trained to respect participants' wishes regarding their participation in the study or certain aspects of the study's procedure. There is minimal, if any, additional risk in having EEG data recorded; EEG is a safe and painless noninvasive technique that is routinely used in clinical medicine.

Benefits

Participants may benefit by feeling a reduction in their cravings for opiates. However, we cannot guarantee that they will benefit. The main benefits of this study are to help researchers and clinicians develop a better understanding of craving and substance use after starting opioid treatment.

7.b. Collection and reporting of AEs and SAEs

See 6.a

7.c Management of SAEs and other study risks

See 6.a and 7.a.

8. Trial Efficacy

8.a Plans for interim Analysis of efficacy data

Go/no go criteria for the UG3 phase will be demonstration of greater FMRI change in any node of the CR or CCN networks or enhanced frontal theta power during a WM task AND greater change in subjective craving measured during a cue reactivity task or outside the FMRI following the tDCS+CCN priming intervention compared to sham tDCS+CCN priming.

9. DSM Plan Administration

9.a Responsibility for data and safety monitoring

The Data Safety Monitoring Board will be comprised of 2 individuals independent from this research project. No member of the board will be a collaborator with the MPI on any other studies or have co-published with the MPIs in the past 3 years. They will be qualified to review the patient safety data generated by this study.

They will review rates of adverse events to determine any changes in participant risk and will make appropriate recommendations for changes in protocol, which will be submitted to the Butler Hospital IRB and NIDA for review.

9.b Frequency of DSM

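### The n-back d' is mis-stated in direction and divisor and has no rule for rates of 0 or 1; the effect is confined to working-memory scores and possible covariate use

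*Combined protocol and SAP*

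**What the plan says.** The scoring rule is in section 4.c of the combined protocol and SAP, under Working Memory and EEG Summary Indices. That paragraph gives d' its role: "Working memory performance at each assessment will be represented by d" (prime). It then sets the scope: "For each participant, and within each n- condition, values for d' will thus be calculated". The conditions in this EEG task are 0-back and 2-back. The rule is that d' is "calculated by dividing the difference of Z (false alarms) and Z" of hits, "by the root mean square of 2". The paragraph ends by saying that d' reflects "the participant's ability to discriminate between the two stimulus types", which it identifies as target and non-target letters.

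It does not say whether Z is a lower- or upper-tail deviate, which direction of d' is better, or what to do when a hit or false-alarm rate is 0 or 1.

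The inferential weight lies elsewhere. In the same paragraph, "Comparison of pre- versus post-treatment Δtheta will test the primary hypothesis". Under EEG outcome measures analyses, the ANCOVA asks whether "there is a statistically significant difference in in the EEG outcome (Δtheta) across treatment groups". The EEG part of the go/no-go rule in sections 2.a, 2.b and 8.a is "enhanced frontal theta power during a WM task".

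**The concern.** Telling targets from non-targets is a yes/no detection task, for which d' is Z(hit rate) minus Z(false-alarm rate). The written rule departs from this in two ways and leaves one gap.

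- **Direction.** False alarms come first. With the usual Z, a participant who discriminates well gets a negative score, and one who improves gets a lower score. That conflicts with the paragraph's own description of d' as an ability.
- **Divisor.** A √2 divisor belongs to two-alternative forced choice, not to the task described. The words used are not √2 either: the root mean square of the single number 2 is 2.
- **Edge rates.** Z is infinite at 0 and 1, and no correction is given. This is a separate omission, most likely to matter in the easy 0-back.

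At stake are the published working-memory scores, since d' is the only stated measure of that performance, and whether two analysts following the text would get the same numbers.

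**Working it through.** **Inputs.** From section 4.c: the order of the two terms, the divisor wording, and the target/non-target description. The documents give no hit rates, false-alarm rates or trial counts, so all of those below are assumptions. The plan states no d' value to reproduce.

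**Step 1: formulas.** H is the hit rate, F the false-alarm rate and Z the inverse normal CDF.
- Standard: Z(H) − Z(F)
- As written, divisor √2: [Z(F) − Z(H)]/√2
- As written, divisor 2 (the literal root mean square, √(2²/1) = 2): [Z(F) − Z(H)]/2
- As written, but Z an upper-tail deviate: [Z(1−F) − Z(1−H)]/√2

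**Step 2: one case in full.** H = 0.85 and F = 0.10 give Z(H) = 1.036 and Z(F) = −1.282. Standard: 1.036 + 1.282 = 2.318. As written: −2.318/1.414 = −1.639, or −2.318/2 = −1.159.

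**Step 3: across assumed rates.**

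| H / F | Standard | Written, ÷√2 | Written, ÷2 | Upper-tail Z, ÷√2 |
|---|---|---|---|---|
| 0.80 / 0.20 | 1.683 | −1.190 | −0.842 | 1.190 |
| 0.85 / 0.10 | 2.318 | −1.639 | −1.159 | 1.639 |
| 0.90 / 0.10 | 2.563 | −1.812 | −1.282 | 1.812 |
| 0.95 / 0.05 | 3.290 | −2.326 | −1.645 | 2.326 |

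As performance improves down the table, standard d' rises and the written index falls. The last column shows that an upper-tail Z restores the sign and leaves only the scale wrong.

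**Step 4: what the divisor does to inference.** It is a constant: 1/√2 = 0.707, or 1/2 = 0.5. Multiplying every score by a constant multiplies mean differences and standard deviations alike. As a check, data were simulated for two groups of 24 (the group size in section 2.d) and compared before and after multiplying by −1/√2. The t statistic went from 3.899 to −3.899, p stayed at 0.00031, and the standardised difference went from 1.125 to −1.125. Only the sign changed.

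**Step 5: edge rates.** Z(0) and Z(1) are infinite under every version, the standard one included. If trials are independent, the chance of a perfect hit rate is H to the power of the number of targets. With 10 to 30 targets and H from 0.80 to 0.99, it runs from 0.80^30 = 0.001 to 0.99^10 = 0.904. That range is too wide to support any statement of how often this would occur.

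**Step 6: where d' is used.** The EEG hypothesis and ANCOVA use Δtheta. The go/no-go rule uses fMRI change or frontal theta, together with craving. The UH3 analyses in 4.c concern subjective and fMRI measures, days of drug use and relapse. The power statements in 2.d do not involve d'. One indirect route remains: the EEG ANCOVAs admit baseline variables that differ by arm, or that predict attrition, at p < 0.05, with no closed list. Baseline d' could qualify.

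**The case against.** The strongest reply is that this is loose prose about a descriptive index. The difference of two quantities does not strictly fix which is subtracted, Z is undefined, and an upper-tail Z makes the written order correct. The same sentence calls d' an ability, so an analyst would expect higher to be better, and a sheet of negative scores from competent participants would be noticed at once. This stands as a reason not to treat the reversal as certain. It does not rescue the text: a scoring rule should not need its reader to choose a definition of Z to get the sign right, and the divisor is wrong for this task under either definition.

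A reader might infer more, in three ways that the documents do not support.

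- **A tDCS benefit would be reported as harm.** The plan contains no between-arm test of d', so no stated conclusion can be reversed.
- **Losing infinite scores would bias the pre-post comparison.** No pre-post comparison of d' is specified, and the plan does not say that infinite values would be dropped.
- **Perfect scores are undefined because of the order or divisor.** The standard formula is just as undefined there. The fault is the missing correction.

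As a covariate, baseline d' with the wrong sign or scale would give the same adjusted treatment effect. Infinite baseline values are different: they could remove participants from that model or stop it from fitting.

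**Conclusion.** The concern holds as a minor error of specification. Read with the usual Z and in the written order, the index is reversed. Raw values are 0.71 or 0.5 of standard in magnitude, depending on how the divisor is read. The reversal rests on that definition of Z; the divisor error does not. The rescaling changes no p-value or standardised effect and matters only when raw scores are set beside standard d' values.

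The missing edge rule is a real but separate gap of unknown frequency. The reach of all three faults is the reported working-memory scores and, if baseline d' qualifies, the covariate set of the EEG ANCOVAs. The specified theta, fMRI, craving and relapse tests and the go/no-go decision do not use d'. The source cited for d' was not available and plays no part in this conclusion.

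**What to change.** Replace the scoring sentence in section 4.c with: d' = Z(hit rate) − Z(false-alarm rate), where Z is the inverse of the standard normal CDF, with no divisor and with higher values meaning better discrimination.

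Add one pre-specified edge correction, applied to every participant and condition. The log-linear form is one acceptable choice: hit rate = (hits + 0.5)/(targets + 1) and false-alarm rate = (false alarms + 0.5)/(non-targets + 1). Under it, a perfect score is finite: about 3.67 with an assumed 10 targets and 20 non-targets, and about 4.54 with 30 and 60. State the actual target and non-target counts as well, because this ceiling depends on them.

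The cost is one sentence in the plan, one line of code and slight shrinkage of extreme scores. No sample size, primary test or go/no-go criterion changes.
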